5.4. Secondary Endpoint(s) Analysis

All secondary efficacy analyses will be based on the full analysis set. Data from participants on placebo in subsequent cohorts will be combined with those from the previous cohort(s) only if the secondary endpoint of those treated with placebo are comparable between cohorts. Where placebo groups are comparable, descriptive statistics for the placebo groups within each cohort will be presented to demonstrate comparability prior to combining the placebo groups.

5.4.1. Percent reduction in the double-blind monthly seizure count

5.4.1.1. Definition

A secondary efficacy endpoint is the percent reduction in the double-blind monthly seizure count which is defined as $100*(Baseline\ monthly\ seizure\ count\$ - Double-blind monthly seizure count is defined as the total number of observable focal onset seizures occurring during the 12-week double blind treatment period, multiplied by $28/X_{DB}$, where X_{DB} is the number of days comprising the double-blind period. A positive percentage change in the double-blind monthly seizure count indicates improvement. The number of seizures experienced by participants who exit the study at Week 4 (i.e. after reaching the baseline seizure count) will be either equal to or larger than their baseline monthly seizure count. Therefore, their observed % seizure rate reduction will either be zero, or negative (implying an increase). For participants who discontinue during the double-blind phase, the actual seizure frequency up to the day of discontinuation will be used.

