# 9.1. Sample Size Determination

The calculation of the maximum sample size planned for this study was simulation-based and was estimated using a Cox's proportional hazard regression model comparing the time to baseline seizure count between JNJ-40411813 and placebo. A longitudinal model for individual daily seizure counts, taking into account between-subject variability in baseline seizure rate and response to treatment, and a residual overdispersed Poisson error was applied. The simulated daily seizure count data were then converted to time to baseline count data and analyzed using a Cox's proportional hazard regression model.

Assuming a placebo median percentage seizure rate reduction of 15% and a further reduction of 50% (respectively 30%) for JNJ-40411813, a cohort with 40 participants randomized to JNJ-40411813 and 20 to placebo would achieve a power of 99% (respectively 83%) at the  $\alpha$ =5% one-sided significance level. In subsequent cohorts with 40:10 randomization, the power becomes 94% for a 50% reduction, with all other assumptions unchanged.

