Participants who meet study entry criteria at the end of the prospective pretreatment baseline period will be randomized to JNJ-40411813 or placebo, CCI. The dosage(s) of concomitant AEDs should not be increased, and new concomitant AEDs should not be added to the treatment regimen. Central randomization will be implemented in this study. Participants will be randomly assigned to one of two treatment groups (JNJ-40411813 or Placebo) based on computer-generated randomization schedules prepared before the study by, or under the supervision of the sponsor. The randomization will be balanced by using randomly permuted blocks stratified by the prescribed baseline

Dosages of JNJ-40411813 in the first cohort will be CCI or placebo for or placebo for . Dosages of JNJ-40411813 in Cohort 2 will and Co be or placebo for or placebo for 7 days, dose increase or placebo on day 8) and . In the following for cohorts, the dose of JNJ-40411813 will be determined based on an ongoing assessment of tolerability and safety results from the previous cohort. The highest dose in following cohorts will for . The highest dose selected to be administered by induced participants will be expected not to exceed the 95th percentile of the plasma Cmax for JNJ-40411813, based on a population PK and/or PBPK model, after repeated administration of The minimum dose that might be considered in successive cohorts will be

Participants are encouraged to complete at least the first 4 weeks of treatment when there are no safety concerns. Participants who have exceeded their pre-randomization monthly seizure count at Week 4, or within any 4-week interval after Week 4 ("4-week sliding window approach") up to Week 12, will have the option to discontinue the study drug for lack of efficacy and to perform the end of study/early withdrawal visit, to continue double blind treatment, or to enter the OLE period. Participants who have not exceeded the pre-randomization seizure count will continue the double-blind treatment period through Week 12 and will have the option to perform the end of study visit or to enter the OLE period.

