5.3. Primary Endpoint(s) Analysis

The primary efficacy endpoint will be evaluated at a 1-sided significance level of 0.05. For all other efficacy endpoints, no multiplicity adjustment will be done.

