5.4.1.2. Analysis Methods

Descriptive statistics (N, mean, SD, median, 25^{th} percentile and 75^{th} percentile) of the percent reduction in the double-blind monthly seizure rate will be summarized for each cohort by treatment group (JNJ-813 or Placebo) pooled over the distribution of the percent reduction in the double-blind monthly seizure count will be categorized into the following levels: $\leq 0\%$ to < 25%; $\geq 25\%$ to < 50%; $\geq 50\%$ to < 75%; $\geq 75\%$ to < 100%; > 100% (seizure freedom). A bar graph of the proportions of participants within each category will be presented by treatment group and stratum.

For each cohort, the percent reduction in the double-blind monthly seizure rate will be analyzed using an ANCOVA model containing treatment group and as factors. Treatment effect will be estimated based on the difference of the treatment group least-square (LS) means with 95% confidence interval. If the nature of the outcome is nonparametric, the percentage reduction will be analyzed using a Wilcoxon rank-sum test.

A sensitivity analysis will be performed where participants who discontinue the study during the double-blind phase and whose double-blind monthly seizure count does not exceed their baseline

monthly seizure count are assumed to have no change in seizure frequency (0% reduction in seizure frequency) even if they reported no seizures prior to discontinuing. The percent reduction will remain the same for those participants whose double-blind monthly seizure count was greater than their baseline monthly seizure count (i.e. increase in seizures) at the time of discontinuation.

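### Percent reduction is measured up to an exit triggered by a high seizure count, so the treatment contrast shifts with exit uptake, in a direction that differs between means and medians

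*SAP*

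**What the plan says.** **Exit rule.** Under SAP 1.2 and Protocol 4.1, a participant whose count exceeds the pre-randomization monthly count at Week 4, or in any later 4-week window, "will have the option to discontinue the study drug for lack of efficacy". The participant may instead continue double-blind treatment or move to the open-label extension. Uptake is not projected.

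**Measurement period.** SAP 5.4.1.1 scales the double-blind count to 28 days. For anyone who discontinues, it uses the frequency observed up to that day. SAP 5.3.1 uses the whole double-blind period for those who stay. Of participants leaving at Week 4 after reaching the baseline count, SAP 5.4.1.1 says: "Therefore, their observed % seizure rate reduction will either be zero, or negative (implying an increase". It does not note that the high count is what ended the period.

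**Estimator.** SAP 5.4.1.2 specifies an ANCOVA: "Treatment effect will be estimated based on the difference of the treatment group least-square (LS) means with 95% confidence interval". Medians and quartiles are descriptive. If the outcome is judged nonparametric, a Wilcoxon test replaces the ANCOVA.

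**Sensitivity analysis.** Also in SAP 5.4.1.2: discontinuers not above baseline are set to 0% reduction, and those above baseline keep their value. The entry for SAP version 4.0 in the version history calls this imputation rule more conservative.

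**Status.** Protocol 9.2.2 treats secondary endpoints as exploratory. Protocol 4.2 says they are there to allow comparison with historical trials.

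**The concern.** The observation period is ended by the quantity being measured. A participant who leaves straight after a bad 28 days is recorded at that level, although the rate might have fallen back by Week 12. One who stays after an equally bad month is averaged over 12 weeks. Exit eligibility differs by arm when the drug works, so the distortion need not cancel in the treatment contrast.

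What is at stake is the effect size on the scale meant for historical comparison. An estimate that moves with the uptake of an optional exit is not like-for-like with trials that lack that exit.

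**Working it through.** **1. Definition.** Let B be the baseline monthly count, C(X) the seizures in Days 1 to X, and X the last double-blind day (84 for a completer). Percent reduction is 100 × [1 − C(X) × (28/X) / B].
- Exit at Week 4: X = 28 and C(28) > B, so the value is negative.
- Later exit: only the latest 28-day window must exceed B, so the average from Day 1 can still lie below B. In the simulation, with drug effect from Day 1, 27-38% of placebo exiters and 44-62% of active exiters still show a positive reduction.

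**2. The plan's own figures.** The documents give none for this endpoint. Protocol 9.1 gives power for the primary endpoint at one-sided 5%: with 40:20 allocation, 99% for a 50% effect and 83% for a 30% effect; with 40:10, 94% for a 50% effect. The planning model is described as "taking into account between-subject variability in baseline seizure rate and response to treatment, and a residual overdispersed Poisson error was applied", without its variance components. With response log-SD 0.3 and overdispersion 2.5, I obtain 98.9%, 68.6% and 93.6% for the stated 99%, 83% and 94%. With 0.15 and 1.5, the 83% reproduces (83.4%) but the 94% becomes 99.1%. No setting tried gave all three. With the components unpublished, this does not show the stated power to be wrong, and nothing below rests on it.

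**3. Simulation.**
- From the documents: 56-day baseline; inclusion criterion 7 (3 to 100 seizures in each 4-week half, no seizure-free interval over 21 days); 84 treatment days; 15% placebo reduction; a further 50% or 30% on drug; the exit rule.
- Assumed: median baseline 10 per 28 days before screening, log-SD 0.9; response log-SD 0.15 to 1.0; daily overdispersion 1.5 to 3; onset at Day 1, Week 2 or Week 4; uptake 25%, 50% or 100% of those eligible.
- Mean differences are unadjusted, because the name of the ANCOVA stratum is redacted. Exits for other reasons are left out.

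Results with every eligible participant exiting (full 84 days → truncated at exit, percentage points):

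| Effect, onset, response log-SD | Exits, placebo / active | Mean difference | Median difference |
|---|---|---|---|
| 50%, Day 1, 0.3 | 66% / 19% | 45.2 → 48.2 | 41.7 → 49.5 |
| 50%, Day 1, 1.0 | 59% / 34% | 71.5 → 72.6 | 42.6 → 51.3 |
| 50%, Day 1, drug effect varying between participants | 68% / 20% | 45.4 → 49.7 | 45.2 → 52.3 |
| 30%, Day 1, 0.3 | 66% / 38% | 26.9 → 28.0 | 24.8 → 31.2 |
| 30%, Day 1, 0.8 | 60% / 45% | 36.1 → 35.9 | 25.0 → 32.7 |
| 50%, Week 2, 0.3 | 67% / 27% | 38.2 → 35.2 | 35.4 → 43.2 |
| 50%, Week 4, 0.3 | 66% / 42% | 30.5 → 15.7 | 27.8 → 33.0 |
| 30%, Week 4, 0.3 | 67% / 51% | 17.7 → 7.8 | 17.1 → 16.9 |

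At log-SD 0.4, a 50% effect from Day 1 gives exits of 66% and 24%, means 47.3 → 49.6 and medians 42.1 → 50.3. Week 2 onset gives means 39.1 → 33.9, and Week 4 onset 30.6 → 12.3. Over all Day 1 settings, the mean shift is −0.2 to +4.3 and the median shift +6 to +11.

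**4. Why means move less.** In the first row the average shift per exiter is about −10 on placebo and −18 on active. Placebo: 0.66 × (−10) = −6.6, against a simulated 3.2 − 9.5 = −6.3. Active: 0.19 × (−18) = −3.4, against 51.3 − 54.7 = −3.4. The net change is about +3. The more frequent placebo exits are partly offset by a larger distortion per active exit.

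**5. Uptake.** In the first row, 50% uptake gives +1.4 (mean) and +3.4 (median); 25% gives +0.7 and +1.5. At Week 4 onset (50% effect), 50% uptake gives a mean shift of −7.7 instead of −14.7.

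**6. No effect.** Exits are 65% in both arms, with no bias and one-sided rejection of 4.4-5.4%.

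**7. Planned sensitivity analysis, first row.** The mean difference is 49.4 (full period 45.2) and the median difference 58.6 (full period 41.7). With so many placebo exiters at 0% or below, the placebo median falls to 0.

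**8. Responder rate.** The difference between arms goes from 44.4 to 44.0 points (50% effect, Day 1, log-SD 0.4).

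**9. Alternatives (50% effect, no exit → all exit).**
- Negative binomial model of the total count with log(days) offset, rate ratio: 0.492 → 0.489 (Day 1), 0.577 → 0.635 (Week 2), 0.675 → 0.853 (Week 4).
- Count model by 28-day period with treatment-by-period terms: within about 0.02 of the no-exit ratio at every onset tried, for example 0.681 → 0.664 at Week 4.
- Days 1-28 percent reduction: mean difference 45.0 against 45.2 over 84 days with Day 1 onset, but 23.8 against 39.1 with a 28-day build-up, and about −1 against 30.2 with Week 4 onset.

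**The case against.** A reader might infer that the plan necessarily overstates the drug's effect. The documents do not support that. The planned estimate is a difference in means, on which the distortion is small if the drug acts from Day 1 and reverses if it acts later. Later action is plausible from the documents themselves: Protocol 2.2.2 puts steady state at 2 to 4 weeks, Cohort 2 has a Day 8 dose step, and SAP 5.5.3 explores delayed effect. The large overstatement is on medians, which the SAP reports only descriptively. This stands, and it limits the point to an unstable contrast without a fixed sign.

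A reader might also take the quoted sentence to mean that every efficacy exit is recorded at zero or worse. It covers Week 4 exits only, and many later exiters keep a positive value.

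Further, exit is optional, those who continue contribute all their data, and the endpoint is secondary and exploratory. All of this stands and limits the consequence. It does not remove the problem: SAP 5.4.1.2 offers no analysis that handles a period ended by a high count, and its one sensitivity analysis moves further from the full-period value when the effect starts on Day 1.

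Finally, the customary percent reduction is needed for historical comparison, and a Days 1-28 summary alone would change the question to four-week efficacy. That also stands, so the remedy should supplement the planned analysis.

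**Conclusion.** The concern holds as a distortion that depends on exit uptake and has no fixed direction. With every eligible participant exiting:
- Effect from Day 1: the median difference is overstated by roughly 6 to 11 points and the mean difference by about 0 to 4.
- 50% effect with delayed onset: the mean difference is understated by about 3 to 5 points (Week 2) or 15 to 18 points (Week 4). The median difference is usually still overstated; the 30%, Week 4 case is an exception.

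About half of each shift remains at 50% uptake. These sizes rest on assumed variance components, onset and uptake, none of which the documents give. That the period ends on a high run, and that the planned sensitivity analysis keeps those values, follows from the text alone.

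Type I error is not inflated. The primary endpoint is unaffected because it uses no data after the baseline count is reached, and the responder rate barely moves. The point deserves a change to the SAP because this endpoint is meant for comparison with other trials.

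**What to change.** Keep the planned full-period percent reduction for historical comparison, and add to SAP 5.4.1.2:

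1. A supplementary likelihood-based overdispersed count model (negative binomial, or Poisson with a participant random effect) of seizures by 28-day period. Include log(days observed in the period) as offset, log baseline monthly count, the randomisation stratum and treatment-by-period terms. Report the rate ratio per period and averaged over 12 weeks. A single total count with a log(days) offset is not enough, because exit biases it when the effect is delayed.
2. Percent reduction on Days 1-28 for all participants, labelled as an early-effect summary free of the efficacy exit and not as a replacement for the 12-week result.
3. The number and timing of lack-of-efficacy exits by arm.
4. Wording that does not present the 0% imputation as conservative for the treatment difference.

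The cost is SAP text, one model and one table, with no change to trial conduct. The supplementary results may look less favourable than the planned median difference.

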5.4.1.2. Analysis Methods

Descriptive statistics (N, mean, SD, median, 25^{th} percentile and 75^{th} percentile) of the percent reduction in the double-blind monthly seizure rate will be summarized for each cohort by treatment group (JNJ-813 or Placebo) pooled over the distribution of the percent reduction in the double-blind monthly seizure count will be categorized into the following levels: $\leq 0\%$ to < 25%; $\geq 25\%$ to < 50%; $\geq 50\%$ to < 75%; $\geq 75\%$ to < 100%; > 100% (seizure freedom). A bar graph of the proportions of participants within each category will be presented by treatment group and stratum.

For each cohort, the percent reduction in the double-blind monthly seizure rate will be analyzed using an ANCOVA model containing treatment group and as factors. Treatment effect will be estimated based on the difference of the treatment group least-square (LS) means with 95% confidence interval. If the nature of the outcome is nonparametric, the percentage reduction will be analyzed using a Wilcoxon rank-sum test.

A sensitivity analysis will be performed where participants who discontinue the study during the double-blind phase and whose double-blind monthly seizure count does not exceed their baseline

monthly seizure count are assumed to have no change in seizure frequency (0% reduction in seizure frequency) even if they reported no seizures prior to discontinuing. The percent reduction will remain the same for those participants whose double-blind monthly seizure count was greater than their baseline monthly seizure count (i.e. increase in seizures) at the time of discontinuation.

5.4.2. Seizure Freedom

5.4.2.1. Definition

A secondary efficacy endpoint is the proportion of participants with seizure freedom where seizure freedom is defined as having no seizures over the complete double-blind period. Participants who record any seizures in the DB period, whether they complete or not, will be included in this analysis (i.e., they will be in the denominator).

5.4.3. Responder rate

5.4.3.1. Definition

A secondary efficacy endpoint is the responder rate which is defined as a participant having at least a 50% reduction of the monthly seizure rate during the double-blind period. The percent reduction in the double-blind monthly seizure count is defined in Section 5.4.1.1. A participant is defined a responder (yes=1) if the percent reduction in the double-blind monthly seizure count is \geq 50%. Participants who do not meet such a criterion will be considered as non-responders and will be assigned a value of 0 (i.e. No). Participants who exit the study at Week 4 after reaching the baseline seizure count will be treated as non-responders in this analysis.

5.4.3.2. Analysis Methods

For each cohort, the number and percentage of participants who achieve a response during the double-blind period will be summarized by treatment group (JNJ-813 or Placebo) pooled over and also treatment group by The treatment effect point estimate (odds ratio) and 2-sided 95% confidence interval will be provided using a logistic regression model containing treatment group and as factors.

Exact logistic regression will be used if the number with seizure freedom is small. If it is not possible to obtain estimates, then Fishers exact test will be used providing point estimate and 95% confidence interval for the percentages.

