3. SAMPLE SIZE DETERMINATION

The calculation of the maximum sample size planned for this study was simulation-based and was estimated using a Cox's proportional hazard regression model comparing the time to baseline seizure count between JNJ-40411813 and placebo. A longitudinal model for individual daily seizure counts, taking into account between-subject variability in baseline seizure rate and response to treatment, and a residual over-dispersed Poisson error was applied. The simulated daily seizure count data were then converted to time to baseline count data and analyzed using a Cox's proportional hazard regression model.

Assuming a placebo median percentage seizure rate reduction of 15% and a further reduction of 50% (30% in a scenario with less efficacy) for JNJ-40411813, a cohort with 40 participants randomized to JNJ-40411813 and 20 to placebo would achieve a power of 99% (83% for the less

efficacy scenario) at the α =5% one-sided significance level. In subsequent cohorts with 40:10 randomization, the power becomes 94% for a 50% reduction, with all other assumptions unchanged.

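### The responder analysis switches to exact logistic regression on the count of seizure-free participants, not responders, so it would probably use the exact method even when responders are not sparse.

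*SAP*

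**What the plan says.** SAP 5.4.3.1 defines the outcome: "A participant is defined a responder (yes=1) if the percent reduction in the double-blind monthly seizure count is" at least 50%. SAP 5.4.3.2 states the main analysis: "The treatment effect point estimate (odds ratio) and 2-sided 95% confidence interval will be provided" from a logistic model with treatment group and one further factor, which is redacted. Two fallbacks follow. The first is "Exact logistic regression will be used if the number with seizure freedom is small". The second is "If it is not possible to obtain estimates, then Fishers exact test will be used".

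Both fallback sentences also stand, word for word, in SAP 5.4.2.2. There the modelled outcome is seizure freedom, and SAP 5.4.2.1 says "seizure freedom is defined as having no seizures over the complete double-blind period". Neither section gives a number for small. Neither document states an expected seizure-free or responder rate. Protocol 9.2.2 leaves the details of the responder analysis to the SAP.

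**The concern.** A switch from an ordinary to an exact logistic model is meant for sparse outcome data. Here the outcome is response, but the switch looks at seizure freedom. The two counts can differ greatly. To be randomized, a participant must have at least 3 seizures per 28 days in each half of baseline and no seizure-free interval over 21 days (Protocol 5.1, criterion 7). Twelve weeks without a seizure is therefore a demanding outcome, while a halving of the rate is the kind of effect the trial is planned around.

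A programmer who follows the text would probably use the exact method when the responder table does not call for it. One who departs from the text makes an unplanned choice of method, possibly after the data are unblinded. At stake are the width of the responder interval and the clarity of the prespecification.

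**Working it through.** **Plan's own figure.** There is none for this endpoint, so nothing can be reproduced first. The documents do give the cohort sizes ("a cohort with 40 participants randomized to JNJ-40411813 and 20 to placebo would achieve a power of 99"% for Cohort 1; "In subsequent cohorts with 40:10 randomization, the power becomes 94% for a 50% reduction" later) and the planning effect ("Assuming a placebo median percentage seizure rate reduction of 15% and a further reduction of 50"%, or 30% in the weaker scenario).

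**Step 1: how often the switch fires.** Assume that small means 4 or fewer seizure-free participants in the cohort, and let the seizure-free rate p vary. The probability is that of a binomial count of at most 4:

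| p | N = 60 | N = 50 |
|---|---|---|
| 1% | 100% | 100% |
| 3% | 97% | 98% |
| 5% | 82% | 90% |
| 10% | 27% | 43% |

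To judge which p is plausible, daily counts were simulated with the eligibility rules and the planning effect. The assumptions, which are not in the documents, were a median of 10 seizures per 28 days, a between-patient log-SD of 0.9, a response log-SD of 0.5 to 1.1 and dispersion of 1.5 to 2.5. The mean seizure-free total per cohort was 0.1 to 1.6, and a total of 4 or fewer occurred in 97 to 100% of runs. Responders averaged 41 to 62% on active and 20 to 34% on placebo. These settings give lower primary power than the plan states, so the sponsor's model may be less variable. Within the simulation, less variable response made seizure freedom rarer still.

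**Step 2: what the switch costs.** With a of n1 responders on active, c of n0 on placebo, b = n1 − a and d = n0 − c:

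- Wald: log(ad/bc) ± 1.96 √(1/a + 1/b + 1/c + 1/d).
- Exact: conditional limits from the non-central hypergeometric distribution.
- Width ratio: log(upper/lower) exact, divided by the same for Wald.

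For 18/40 against 6/30 (placebo pooled, 20 + 10), OR = (18 × 24)/(22 × 6) = 3.27. SE = √(1/18 + 1/22 + 1/6 + 1/24) = 0.556. The Wald limits are exp(1.186 ± 1.090).

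| Responders | OR | Wald 95% CI | Exact 95% CI | Width ratio (log) |
|---|---|---|---|---|
| 18/40 vs 6/30 | 3.27 | 1.10 to 9.74 | 0.99 to 11.8 | 1.13 |
| 20/40 vs 5/20 | 3.00 | 0.92 to 9.83 | 0.81 to 12.4 | 1.15 |
| 16/40 vs 4/20 | 2.67 | 0.75 to 9.45 | 0.67 to 12.8 | 1.16 |
| 16/40 vs 2/10 | 2.67 | 0.50 to 14.2 | 0.44 to 28.5 | 1.25 |

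Averaged over all tables at assumed response rates of 20 to 60% on active and 15 to 30% on placebo, the exact interval is 15 to 22% wider at 40:20 and 23 to 30% wider at 40:10.

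**Step 3: whether the exact method is needed.**

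- At 40:20 the chance of an empty cell is 0.1 to 4%, and Wald coverage when no cell is empty is 96 to 97%. The ordinary model is adequate. At 50% against 20% responders, the lower limit exceeds 1 with probability 62% (Wald) and 53% (exact).
- At 40:10 the chance of an empty cell is 3 to 20%. At the same rates the lower limit exceeds 1 with probability 22% (Wald, counting empty-cell tables as failures) and 28% (exact). Here the exact method can be the better choice.

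All tables omit the redacted model factor.

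**The case against.** Several points on the other side are sound.

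- A reader might infer that the switch will almost always fire. The documents do not support that: small has no cut-off and no seizure-free rate is given. Two SAP rules also push the seizure-free count up. Missing diary days count as seizure-free (5.3.1), and dropouts with no recorded seizure are counted as not seizure-free only in a sensitivity analysis (5.4.2.2). At a 10% rate and a cut-off of 4, the switch would usually not fire.
- A reader might also infer that the widening is always needless. That holds at 40:20 and with pooled placebo. It does not hold in general for a 40:10 cohort analysed on its own, where 2 placebo responders of 10 is an ordinary result. The omitted factor makes the real tables sparser still.
- The error leans to the safe side. Every seizure-free participant is also a responder, so scarce responders imply scarce seizure freedom. The switch tends to fire too often, and the exact interval keeps its coverage. This argument does not extend to scarce non-responders.
- The stakes are modest. SAP 5.3 makes no multiplicity adjustment for this endpoint, and Protocol 9.2.2 describes secondary analyses as exploratory. Counts and percentages are reported whichever model is used. The loss of exclusion of 1 in the 18/40 against 6/30 table is one illustration, with no decision rule attached.

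These points limit the size of the problem. None makes the seizure-freedom count a suitable trigger for the responder model, and neither redaction nor another section explains the sentence.

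**Conclusion.** The point holds as an error of specification with a limited consequence. The method for the responder odds ratio is governed by the wrong endpoint's count. Under the entry criteria the rule would probably impose the exact method where responders are not sparse. The cost is an interval about 15% wider on the log scale at 40:20 or with pooled placebo. At 40:10 with unpooled placebo there may be no real cost. The interval remains valid, and nothing here bears on the primary conclusion.

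The mismatch itself is plain from the text. That the switch will probably fire rests on an assumed cut-off of 4 and an assumed seizure-free rate of about 5% or lower. The widths rest on unstratified tables.

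**What to change.** In SAP 5.4.3.2, replace the seizure-freedom trigger with one on the responder data. For example: exact logistic regression only if either treatment group, pooled over strata, has 0 or 1 responders or 0 or 1 non-responders, or if the ordinary model shows separation or does not converge; otherwise the planned logistic model. Fix the rule before unblinding.

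The cut-off should be low. A rule of fewer than 5 in either group would, at a 20% placebo rate, fire 63% of the time with 20 placebo participants and 97% with 10. The 0-or-1 rule fires on placebo with probability 0.8^20 + 20 × 0.2 × 0.8^19 = 7% with 20, and 0.8^10 + 10 × 0.2 × 0.8^9 = 38% with 10, where the exact method is often wanted. With 30 pooled it is 1%.

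The cost is one SAP sentence. The small downside is that the Wald interval is approximate in moderately sparse tables.
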